APPENDIX 4 – List of prohibited strong CYP3A4 inducers and inhibitors	

1. SYNOPSIS

Title	g Mammary Stem Cells and Breast Cancer Prevention		
Design	Design Non-randomized, open-label, phase II, window of opportunity trial.		
	The overall purpose of this study is to determine if rapamycin can reduce malignant markers and MaSC number in surgical specimens.		
Objectives	 The primary objectives are: Reduction of MaSC in DCIS, LCIS, ALH or ADH in patients receiving rapamycin Reduction of malignant markers in DCIS, LCIS, ALH or ADH in patients 		
	receiving rapamycin The secondary objectives are: 1. Toxicity 2. Surgical complications		
Patient Population	Women (pre and post-menopausal) with DCIS, LCIS, ALH or ADH undergoing surgical resection.		
Treatment Plan	Women who consent will be given rapamycin for 5-7 days treatment at 2 mg/day. Patients will undergo mastectomy or lumpectomy 3-7 days after the last dose of rapamycin. Pathological and molecular biomarkers associated with breast cancer aggressiveness and recurrence will be assessed by the Breast Pathologist and the features of MaSCs will be determined by the PI's lab for determining the effect of rapamycin.		
Efficacy Assessment	Efficacy will be measured by measurement of MaSC and malignant markers in tissue from patients with DCIS, LCIS, ALH or ADH		

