Age-associated changes in MaSC frequency and gene expression. Using this SFD assay, we measured MaSC number as a function of aging. FACS analysis revealed that total basal epithelial cell frequency, which is percent of basal epithelial cells in total lineage negative (Lin-) mammary epithelial cells (MEC) (Fig. 1A), increased with progressive aging in C57BI/6 mice (Fig. 2). This aging-associated increase of basal epithelial cells and decrease of luminal epithelial cells (data not shown) led to a significant decrease in the luminal to basal epithelial cell ratio (Fig. 3A) and a significant increase in MaSC frequency (Fig. 3B) in old (22-30 month-old) mice of both C57BI/6 and Balb/c strains when compared to their respective young (4-6 month-old) cohorts. However, the ability of the 3D structures to regenerated 3D structures during serial passage in 3D culture was much lower by the old MaSC-formed 3D structures than by the young MaSC-formed 3D structures (data not shown). To elucidate molecular changes associated with aging MaSCs, we

used RNA-seq to profile whole transcriptome of FACS-sorted basal, luminal, stromal cells, and early stage mammospheres formed by basal or luminal epithelial cells, which are highly enriched in MaSCs or luminal progenitors respectively, from young and old C57BI/6 mice.

Using pairwise comparison among young mammary cells, we obtained a set of basal or luminal cell specific genes/markers, named Basal Signature or Luminal Signature respectively and performed gene signature enrichment analysis (**GSEA**) using the basal or luminal markers we identified as well as those previously reported by Lim et al.²¹. As shown in **Fig. 4**, the old basal (CD49fhighCD24med) cells and their mammospheres showed significantly reduced expression of basal markers, but significantly increased luminal markers. In contrast, GSEA did not show a significant change of the basal or luminal signatures in old luminal (CD49flowCD24high) cells and their mammospheres (data not shown). These findings indicate aberrant changes of old MaSCs towards a more luminal phenotype, which may contribute to their reduced self-renewal capacity and transforming property as described below.

[figure not shown]
[figure not shown]
[figure not shown]

Fig. 2. Representative FACS profiles of Lin MEC (luminal+basal fraction) from C57Bl/6 mice at different ages showing basal MaSC-enriched fraction (purple).

[figure not shown]

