Increased inflammation and immune responses in old mammary cells. As the initial step in elucidating cellular pathways that may contribute to the aging-associated transforming phenotype of MaSCs, we compared gene expression profiles between young and old mammary stromal cells and found that the *Cdkn2a* locus, containing p16Ink4a and p19Arf, was the most highly up-regulated transcript in the old stromal cells among all significantly (adjusted P value (aka **FDR**, false discovery rate)<0.05) and differentially regulated genes with a 19-fold difference (see the heatmap in **Fig. 10**). The significant increase of both p16Ink4a and p19Arf in the old stromal cells was confirmed with real time RT-PCR (**Fig. 7**) suggesting a senescence phenotype of the old stromal cells. This is consistent with the old mammary gland expressing higher senescence-associated β -gal activity (**Fig. 8**). We found 66 differentially expressed genes between young and old stromal cells with an adjusted P value of <0.05 (**Fig. 9**).

Functional annotation of these differentially expressed genes with the Database for Annotation, Visualization and Integrated Discovery (**DAVID**)²² platform identified many significantly (P<0.05) altered Biological Processes (**BPs**) depicted as gene ontology (**GO**) terms with the top ten listed in **Fig. 9**. While over 200 genes were found to be differentially expressed between young and old luminal progenitorenriched spheres, DAVID analysis yielded top enriched BPs mostly related to cell adhesion, biological adhesion, and extracellular matrix organization (data not shown) suggesting that aging-associated luminal cell functions are more involved in epithelium structure remodeling with a limited role in the early neoplastic transformation by the old MaSCs. Consequently, we have focused our attention on the altered gene expression in aging stromal cells and MaSCs. Although there are only 7 genes that are differentially regulated during aging in both basal cell-formed mammospheres and stromal cells (**Fig. 9**), the functional annotation revealed that the top enriched Biological Processes in both sets of the genes are related to immune, inflammatory, defense, and wounding responses (**Fig. 9**).

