These processes and responses are mostly performed by a shared set of genes in each cell type, which are shown in the heatmaps in **Fig. 10**. Some of the genes associated with the Oxidation Reduction, the top GO term for the stromal gene set, are involved in biosynthesis/production of eicosanoids, which may also contribute to inflammation (**Fig. 10**). We have also observed a significant increase of *Ptgs2* transcript in our RNA-seq data (pointed by the arrow in **Fig. 10**) and its protein COX2 in old mammary gland with immunostaining (**Fig. 14** shown in Aim 2.2), and an increased number of infiltrating macrophages in the old mammary gland (data not shown). Thus, there is an increased senescence-associated inflammation response (**SIR**) in the old mammary glands.

[figure not shown]

Fig. 10. Heatmap of the fold change of significantly (FDR<0.05) differentially expressed genes associated with senescence and top three GO terms shown in Fig. 6 between young and old mammosphere and stromal cells. The genes associated with the three GO terms are marked with the colored vertical bars. Heatmap colors indicate the logarithm of the fold change.

Rapamycin treatment mitigated the aberrant phenotypes of old MaSCs. To investigate whether the increased SIR in the old mammary gland contributes to the increased number and transforming phenotype of the old MaSCs, we tested the efficacy of rapamycin in inhibiting the aging-associated mammary gland dysfunction because it is an anti-inflammatory and immune modulatory drug and its target mTOR is known to be up-regulated in senescent cells²³. Rapamycin was shown to significantly extend lifespan and reduce tumor incidence in mice by investigators in our university as well as by others²⁴. It was also shown recently to inhibit senescent mammary stroma-promoted growth of

xenografted breast cancer cells in a premature aging mouse model with *Cav-1* knockout²⁵. As shown in **Fig. 3B**, old mammary glands have higher percent of MaSCs. Both long-term (2 years) and short-term (5-10 days) treatment with a diet containing eRapa (microencapsulated rapamycin) significantly reduced the frequency of MaSCs in old mice (**Fig. 11A**). More significantly, both long- and short-term treatment also reduced hyperplastic and dysplastic foci not only in the primary old mammary glands but also in the regenerated glands by old MaSCs (**Fig. 11B** and **C**).

[figure not shown]

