15.2 Statistical and Data Analysis

Availability of case and justification of sample size. According to our co-investigator and breast pathologist, the surgeons at our cancer center operated 24 cases of DCIS in 2013.

Ages	# of patients at UT Health San Antonio Mays Cancer Center
< 50	7
50-59	10
> 60	7

We consider about 60-70% enrollment in 5-year recruitment duration, we shall be able to recruit about 50-60 patients with menopausal status clinically confirmed. Tissue from this study will be compared to DCIS specimens from patients not treated with rapamycin. These specimens will be collected through the ongoing biorepository.

Statistically significant differences of the histopathological parameters and the molecular markers between the core biopsy and surgical specimens due to the rapamycin treatment will be tested by Mantel-Haenszel test for categorical data with scores ranging from 0 to 4 (or higher) as shown in Figure 2. To reach statistical power >70%, a patient group size of 24 or more is required for us to detect the difference of a score of 0.3 between untreated biopsy and treated surgical specimens with the P value targeted at 0.05 for one-sided Mantel-Haenszel test.

The **Mantel-Haenszel test** (between Rapamycin treatment & non-participant patients) will be set up as follows.

No Rapamycin # of patients (c) # of patients (d) c/(c+d)

Test between treatment & non-participant patients				
Study		IHC score ≤ 2	IHC score > 2	Percentage
UT Health San Antonio	Rapamycin	<pre># of patients (a)</pre>	# of patients (b)	a/(a+b)

Mantel-Haenszel test will allow us to extend IHC score to full range (instead of dichotomizing the IHC score), as well as other sites if more patients will be enrolled at different sites (we will not lump all patients together into one group, in case the underlying population demographic is a concern at different enrollment sites). Significance will be determined at p-value < 0.05 (Chi-square distributed with one degree of freedom). During the recruitment period, we will monitor the IHC scores different from two groups (treated/untreated) with simple *t* test on average IHC score (across all patients within each group) for each marker, in order to assess the IHC effectiveness, enrollment progress and patient demographic parameters and their association to final study outcomes.

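### The comparison of treated women with non-participant biorepository controls makes no allowance for age, so an age imbalance could mimic or mask a rapamycin effect

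*Combined protocol and SAP*

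**What the plan says.** The synopsis describes a "Non-randomized, open-label, phase II, window of opportunity trial" in "Women (pre and post-menopausal) with DCIS, LCIS, ALH or ADH undergoing surgical resection". For the reference group, Section 15.2 says "Tissue from this study will be compared to DCIS specimens from patients not treated with rapamycin" and "These specimens will be collected through the ongoing biorepository". The Mantel-Haenszel table in that section sets rapamycin patients against non-participants, by IHC score up to 2 or above 2. The test may be extended over sites, "in case the underlying population demographic is a concern at different enrollment sites". No other stratum, matching factor or covariate is named. Demographics otherwise appear only in the monitoring planned during recruitment, alongside simple t tests.

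Section 15.2 also plans paired comparisons of core biopsy with surgical specimen, including a McNemar test within each arm.

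Section 3 reports the following in mice:
- **MaSC:** old animals of two strains showed "a significant increase in MaSC frequency".
- **p16:** the *Cdkn2a* locus, which contains p16, "was the most highly up-regulated transcript in the old stromal cells", with a 19-fold difference.
- **COX2:** an increase was seen in the *Ptgs2* transcript and in "its protein COX2 in old mammary gland with immunostaining".

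MaSC and malignant markers are the two primary objectives (Section 4.1). p16 and COX2 are among the IHC markers listed in Section 18. The schedule in Section 13 marks tissue procurement at surgery only.

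**The concern.** Women who agree to take a drug before surgery may differ in age from those who do not take part. If the markers depend on age, a difference in age mix becomes a difference in markers, and the test as written credits it to rapamycin or sets it against rapamycin. At a single site the test has one stratum, so it is an unadjusted 2×2 comparison. The plan accepts the principle for sites, where it declines to pool women whose demographics may differ. It does not apply that principle to treated versus untreated women, where self-selection acts directly.

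For IHC the paired tests offer a second route to an answer. For MaSC no pre-treatment fresh sample is scheduled, so untreated controls are the only reference for a primary objective.

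**Working it through.** The plan gives no figure for this comparison that could be reproduced. The stated 24 patients for power above 70% refer to a 0.3-point difference between biopsy and surgical specimens and come without a standard deviation. They are used below only as a group size.

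**Inputs from Section 15.2**
- Age mix of the 24 DCIS cases operated on in 2013: 7 under 50, 10 aged 50–59, 7 over 60. The share aged 50 or more is (10 + 7)/24 = 71%.
- Group sizes: 24 (stated minimum) and 50 (lower end of expected recruitment).
- Significance at 0.05 on a 1-df chi-square, taken as two-sided.

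**Assumptions**
- Controls have the centre's age mix, and 50% or 40% of treated women are aged 50 or more.
- There are as many controls as treated women (the number of controls is not stated).
- P(IHC score >2) at 50 or more versus under 50 is 70%/30%, 60%/40% or 55%/45%.
- There is no drug effect.

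**Spurious difference** = (control share aged 50+ − treated share aged 50+) × (gradient between age groups). For 70/30 and 50% treated: (0.708 − 0.50) × 0.40 = 0.083.

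**Check by hand, 24 per group.** Controls: 0.708 × 0.7 + 0.292 × 0.3 = 0.583. Treated: 0.50. Standard error = √[(0.583 × 0.417 + 0.25)/24] = 0.143. Shift = 0.083/0.143 = 0.58. Two-sided rejection ≈ P(Z > 1.96 − 0.58) + P(Z < −1.96 − 0.58) = 0.084 + 0.006 = 9%. Simulation gives 10%.

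**Simulation.** The statistic is [Σ(aₖ − Eₖ)]²/ΣVₖ, with Eₖ = n₁ₖmₖ/Tₖ and Vₖ = n₁ₖn₂ₖmₖ(Tₖ − mₖ)/[Tₖ²(Tₖ − 1)]. Here aₖ is the number of treated women scoring up to 2 in stratum k, n₁ₖ and n₂ₖ are the group sizes, mₖ is the number of all women scoring up to 2, and Tₖ is the total. No continuity correction is used. One stratum gives the crude test; two age strata give the adjusted test. Two-sided rejection rates:

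| Gradient | Treated aged 50+ | Spurious difference (points) | Crude, 24/group | Crude, 50/group |
|---|---|---|---|---|
| 70/30 | 50% | 8.3 | 10% | 14% |
| 70/30 | 40% | 12.3 | 15% | 25–26% |
| 60/40 | 50% | 4.2 | 7% | 8% |
| 60/40 | 40% | 6.2 | 8% | 10–11% |
| 55/45 | 50% | 2.1 | 6% | 6% |
| 55/45 | 40% | 3.1 | 6–7% | 7% |

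The age-stratified test rejects about 5% of the time in every row. With no age imbalance the crude test itself rejects 5.4–5.9%, because counts are discrete, so the 55/45 rows show almost no inflation.

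**Opposite imbalance.** If 80% of treated women are aged 50 or more (70/30 gradient), a one-sided 5% test for benefit rejects 3% of the time at 24 per group and 2% at 50. A true effect would be partly masked.

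**Three age bands.** Assume P(score ≤2) of 0.7/0.5/0.3 across the tabulated bands, treated women split 12/8/4 and controls 7/10/7. The crude one-sided test rejects 13% at 24 per group and 18% at 55. The stratified test again stays at about 5%.

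**Cost in power.** With equal age mixes and an assumed odds ratio of 3, one-sided power is 52% stratified versus 51% crude at 24 per group, and 84% versus 81% at 55.

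**The case against.** The strongest reply is that the analysis most prominent in Section 15.2 is paired. A woman's age is effectively the same at biopsy and at surgery, so the within-patient IHC tests cannot be confounded by it. This stands, and it limits the point to the between-group test. A reader might infer that every p16 or COX2 result is at risk; the plan does not support that.

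Second, the age data come from mice, and the p16 finding is a stromal transcript. A reader might infer that the protocol shows age dependence of IHC scores in women's lesions. It does not. The gradients above are therefore assumptions, and a shallow one makes the problem negligible.

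Third, Section 15.2 is silent on how controls are chosen, so it is not established that they will be unmatched or differ in age. Participants must also consent to the biorepository (Section 5.1), so both groups share a source. That may help comparability of specimens, but it does not balance age.

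Fourth, the plan does mention demographic parameters and their association with outcomes. That belongs to monitoring during recruitment and does not adjust the final test.

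Finally, the simulated outcome is a dichotomised IHC score. No test is specified for MaSC, so the MaSC concern rests on the design and has no error rate attached to it.

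**Conclusion.** The point holds for the between-group comparison. Followed as written, that test does not adjust for age in a non-randomised comparison of outcomes that the sponsor's own rationale links to age. Under the assumed imbalances its false-positive rate runs from about 6%, close to nominal, to about 26% with the steep gradient, the larger imbalance and 50 per group. The size depends on a human age gradient and an age imbalance that the documents do not give.

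The direction is also open. A reader might infer that the bias favours rapamycin; it does so only if treated women are younger. The weight of the point comes from MaSC, which has no paired baseline, and from the low cost of the remedy. It is a change that should be made, and it does not show that the study's IHC results would be wrong.

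**What to change.** In Section 15.2, add age group as a stratum of the Mantel-Haenszel test between treated and non-participant patients, either under 50 versus 50 or more, or the three tabulated bands. State that continuous MaSC measures will be compared between groups with age as a covariate. Where records allow, draw controls from the same calendar period as participants.

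It may be tempting to require controls to meet all trial eligibility criteria. That would need hormone, laboratory and medication data that the documents do not show to exist for biorepository women. It would also shrink a small pool: 24 cases a year for 5 years with 60–70% enrolled leaves 120 × 0.30 to 120 × 0.40, or 36–48, DCIS non-participants.

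The cost is a few sentences. The documents do not say what the biorepository records, so controls without a recorded age would be lost. Strata may be sparse at 24 per group, which favours two age groups over three at that size.

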For statistical test within either treatment or control arm, we will use **McNemar's test** to examine IHC score differences between biopsy and surgical tissues (at significance level of 0.05). The 2x2 table set up as follows.

Test within treatment or no treatment

After treatment

		IHC score ≤ 2	IHC score > 2
Before treatment	IHC score ≤ 2	# of patients with	# of patients with
		lower IHC scores before & after	higher IHC score after treatment
	IHC score > 2	# of patients with	# of patients with
		lower IHC score after treatment	higher IHC scores before & after

Similar to between arm test, during the recruitment period, we will monitor the IHC scores different within each arm with simple paired-*t* test on average IHC score difference for each marker, in order to assess the IHC effectiveness, enrollment progress and patient demographic parameters and their association to final study outcomes.

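### As laid out in section 15.2, no test compares biopsy-to-surgery IHC change between treated and untreated women or adjusts the between-group test for biopsy score, so a change cannot be attributed to rapamycin

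*Combined protocol and SAP*

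**What the plan says.** Section 15.2 contains four kinds of comparison of the IHC scores.

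- **Before-after, used for sizing.** Differences "between the core biopsy and surgical specimens due to the rapamycin treatment will be tested by Mantel-Haenszel test". A group of 24 or more is said to give over 70% power, one-sided at 0.05, to "detect the difference of a score of 0.3 between untreated biopsy and treated surgical specimens". No table is printed for this contrast.
- **Between groups.** The untreated comparator comes from the biorepository: "Tissue from this study will be compared to DCIS specimens from patients not treated with rapamycin". The Mantel-Haenszel test ("between Rapamycin treatment & non-participant patients) will be set up as follows") crosses rapamycin or no rapamycin with IHC score at most 2 or above 2. It can be widened: "Mantel-Haenszel test will allow us to extend IHC score to full range (instead of dichotomizing the IHC score), as well as other sites". The table does not say which specimen is scored.
- **Within each arm.** "For statistical test within either treatment or control arm, we will use" McNemar's test of biopsy against surgical score.
- **Monitoring during recruitment.** A t test compares average scores between groups. For the paired scores, "we will monitor the IHC scores different within each arm with simple paired" t tests.

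The synopsis describes the design as non-randomised and open-label. Reduction of malignant markers is a primary objective (section 4.1). Section 18 names p16, COX2 and Ki-67 for both the core biopsy and the surgical specimen. The plan projects that "we shall be able to recruit about 50-60 patients with menopausal status clinically confirmed"; it states no number of controls.

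**The concern.** A core biopsy and a later surgical specimen from the same woman can score differently without any drug. A before-after contrast in treated women alone measures drug effect plus untreated drift. If scores tend to fall without treatment, the contrast that sizes the trial credits that fall to rapamycin. If they tend to rise, a real reduction could be hidden.

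The rapamycin versus non-participant test has a different weakness. If it uses the surgical specimen, which is the natural reading, any difference in score already present at biopsy passes into the result. Women who join a drug trial before surgery may differ from those who do not.

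The information needed to deal with much of this is paired scores in both groups. The within-arm tests already presuppose those scores, but the plan never combines them into one comparison.

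**Working it through.** **1. What each planned test uses**

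| Test in section 15.2 | Treated vs untreated? | Uses biopsy score? |
|---|---|---|
| Biopsy vs surgery (sets n=24) | No | Yes |
| Mantel-Haenszel, rapamycin vs non-participants | Yes | No |
| Monitoring t test on average scores | Yes | No |
| McNemar, each arm | No | Yes |
| Monitoring paired t test, each arm | No | Yes |

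No row has both. A significant result in one arm and a non-significant result in the other is not a test of the difference between arms.

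**2. The plan's own figure.** Inputs from section 15.2: 0.3 points, one-sided 0.05, 70% power, n=24. No SD is given, so 24 can be neither confirmed nor refuted. Solving for the SD it implies, with 1.645 + 0.524 = 2.169:
- paired formula: SD of change = 0.3 × √24 / 2.169 = 0.678 (variance 0.459);
- two-sample formula: SD of score = 0.3 × √12 / 2.169 = 0.479 (variance 0.2295).

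**3. Effect of untreated drift (assumed).** For a one-sided mean-change test with no drug effect, P(reject) = Φ(drift × √24 / SD − 1.645), downward drift positive.
- SD 0.678: drift 0.1 gives Φ(0.723 − 1.645) = 18%; drift 0.2 gives Φ(1.446 − 1.645) = 42%.
- SD 1.0: Φ(0.490 − 1.645) = 12%; Φ(0.980 − 1.645) = 25%.
- Upward drift of 0.1 and 0.2: 0.9% and 0.1% at SD 0.678; 1.6% and 0.4% at SD 1.0.

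For the dichotomised McNemar test I used simulation: 40,000 trials of 24 pairs, rounded normal scores with mean 2.5 and SD 1, cut at above 2. Results for downward drift of 0.1 and 0.2:
- correlation 0.5: a decrease is declared in 4.5% and 8.5% of trials (exact version 2.1% and 4.6%);
- correlation 0.77: 5.7% and 11.4% (exact version 1.6% and 3.8%).

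The nominal rate in that direction is 2.5%.

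**4. Effect of baseline imbalance (assumed).** Simulation with no drug effect, 24 per group, score SD 1, correlation 0.5, two-sided 0.05:

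| Imbalance | Surgical score alone | Adjusted for biopsy | Difference in change |
|---|---|---|---|
| 0.3 at biopsy, lasting | 18% | 9% | 5% |
| 0.3 falling to 0.15 | 8% | 5% | 8% |

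Adjustment improves on the unadjusted test in both cases, but neither alternative holds 5% in both.

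**5. Power of the between-group analyses.** One-sided power = Φ(0.3 / √(V(1/n₁ + 1/n₂)) − 1.645), and n per group for 70% = 2V(2.169/0.3)². The correlations of 0.5 and 0.7 are assumptions.

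*If 24 came from a paired formula:*
- Change, V = 0.459: 46% at 24 per group; 48 per group for 70%.
- Adjusted, V = 0.459(1 + ρ)/2 = 0.344 or 0.390: 55% or 51% at 24 per group; 36 or 41 for 70%.
- Surgical score alone, V = 0.459/(2(1 − ρ)) = 0.459 or 0.765: 46% or 32% at 24 per group.

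*If 24 came from a two-sample formula:*
- Adjusted, V = 0.2295(1 − ρ²) = 0.172 or 0.117: 18 or 13 per group for 70%.
- Change, V = 0.2295 × 2(1 − ρ) = 0.2295 or 0.138: 24 or 15 per group.

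**The case against.** **The opening sentence is ambiguous.** It applies Mantel-Haenszel to biopsy-surgery differences, and the only Mantel-Haenszel layout that follows compares rapamycin with non-participants. The two could be one test of differences between groups. That reading cannot be excluded, but the printed table shows scores by group only, with no change score and no biopsy category. The literal layout is the likelier reading.

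**The plan does look at untreated drift.** A reader might infer that drift is ignored. It is not: McNemar and paired t tests are planned in the control arm too. What is missing is the formal contrast between the two changes.

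**The largest error rates do not belong to the named final tests.** A reader might take 18-42% as the plan's false-positive rate. The documents do not support that. It applies to a one-sided mean-change test under an assumed drift and SD; for the dichotomised McNemar test the simulated rate is about 5-11%, or 2-5% if exact.

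**Adjustment costs power.** It may, relative to the before-after test. How much depends on where 24 came from: under the two-sample reading with a correlation of 0.5 or more, the cost largely disappears. Relative to the unadjusted between-group test already planned, adjustment adds power.

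**A stricter rule might look safer.** One could demand that the adjusted analysis and the difference in change both be significant. That is a preference, not something this gap requires. Its power is lower, and it does not protect against every pattern of imbalance: if a 0.3-point baseline gap vanishes by surgery, its error exceeds 5%.

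**Conclusion.** The gap is real. As laid out, section 15.2 has no between-group test of change and no between-group test adjusted for biopsy score. The contrast behind n=24 has no control term and cannot by itself support attribution to rapamycin; the table that does have controls is open to baseline imbalance.

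The conclusion about structure rests on the text alone. The size does not: every figure above depends on an assumed SD, drift, imbalance or correlation, because the documents give none. It does not follow that 24 is wrong, since without an SD it cannot be checked.

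Two limits apply. The untreated comparator described is DCIS only, so treated LCIS, ALH and ADH have no matched control in this comparison. The MaSC endpoints are outside this point: section 13 schedules fresh tissue only at surgery, so no biopsy baseline is described for them.

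**What to change.** In section 15.2, for each IHC marker scored on both specimens (p16, COX2, Ki-67):

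- Make the attribution analysis the comparison of surgical score between rapamycin-treated and untreated DCIS, adjusted for biopsy score. ANCOVA or proportional odds on the full score would serve, or Mantel-Haenszel stratified by biopsy category.
- State one sidedness. At present the sample size is one-sided, while the analysis uses p<0.05 on a one-degree-of-freedom chi-square, a two-sided form.
- Report the between-group difference in change as a sensitivity analysis, with no requirement that both be significant.
- Label the before-after and McNemar tests supportive, and delete the words that attribute the before-after difference to rapamycin.
- State that n=24 with over 70% power applies only to the before-after contrast.
- State that adjustment reduces but does not remove selection bias from non-participation, and that lesions other than DCIS have no matched control here.
- Confirm that control core biopsies are stained and scored in the same way. The McNemar test in controls presupposes those scores, but section 18 describes tissue collection only from treated patients.

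**Cost.** Text changes plus one model and one change contrast per marker; no added enrolment is proposed. The downside is a possible loss of stated power. On the paired reading, 24 per group gives 51-55% for the adjusted analysis and 46% for change, one-sided (38-43% and 34% two-sided), against 70% for the before-after test. On the two-sample reading with a correlation of 0.5 or 0.7, 24 per group reaches 70% for both.

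### Section 15.2 rests n=24 on a biopsy-versus-surgery Mantel-Haenszel test whose pairing is unspecified; no planned final test uses both the pairing and the full score, and the >70% power cannot be reproduced

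*Combined protocol and SAP*

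**What the plan says.** Section 15.2 of the combined protocol and SAP makes several statements about the same data.

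- **Test that carries the sample size.** Differences "between the core biopsy and surgical specimens due to the rapamycin treatment will be tested by Mantel-Haenszel test for categorical data". The score is said to run from 0 up to 4 or beyond, and the reader is referred to a Figure 2 for it.
- **Sample size.** "To reach statistical power >70%, a patient group size of 24 or more is required". The target is a 0.3-point difference between the two specimens, tested one-sided at 0.05. Accrual of about 50-60 patients is expected.
- **Mantel-Haenszel layout.** The one table shown sets rapamycin patients against non-participants. The text after it says that the method extends to the full score range and to further sites should they enrol: "we will not lump all patients together into one group, in case the underlying population demographic is a concern at different enrollment sites". Significance is then set at 0.05 on a one-degree-of-freedom chi-square.
- **Within-arm test.** Biopsy versus surgical tissue is also given to McNemar's test at 0.05, in a before/after table that splits the score at 2.
- **Monitoring.** During recruitment a paired t "test on average IHC score difference for each marker" is used within each arm.

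No SD, correlation or distribution of scores is given. The Fig. 2 in Section 3 shows mouse cell-sorting profiles, so it does not supply the spread of the score.

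**The concern.** The comparison that sets n is before versus after in the same woman. It addresses the second primary objective in Section 4.1, reduction of malignant markers. An analyst who follows Section 15.2 is not told to match the two specimens in the Mantel-Haenszel test and has only an independent-groups layout to copy. If that layout is used on positively correlated pairs, the standard error is too large, the test rejects too rarely under the null, and a real fall is more likely to be missed than with a paired test.

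The formal paired alternative, McNemar's test, treats a fall from 4 to 3 or from 2 to 1 as no change. The only planned procedure that is both paired and on the full score is the monitoring t test. The power statement is therefore attached to a test whose error term is undefined. Leaving that choice open also allows it to be made after the data are seen.

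**Working it through.** **Inputs from Section 15.2:** n = 24 ("a patient group size of 24 or more is required for us to detect the difference of a score of 0.3"), difference 0.3, one-sided alpha 0.05, power 70%, score 0-4, expected accrual 50-60. **Assumed, because not stated:** SD and within-woman correlation r, shown as ranges. Normal approximation throughout: z(0.05) = 1.645, z(0.70) = 0.524, sum 2.169.

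**1. The plan's own figure.** It cannot be reproduced without a measure of spread, so the calculation is solved backwards for the largest SD that gives 70%.

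- Independent specimens: SD = 0.3 / (2.169 × √(2/n)). At n=24: 0.3 / (2.169 × 0.2887) = 0.48. At n=50: 0.3 / (2.169 × 0.2) = 0.69.
- Paired: SD of change = 0.3 × √n / 2.169. At n=24: 0.3 × 4.899 / 2.169 = 0.68. At n=50: 0.3 × 7.071 / 2.169 = 0.98.

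**2. Size if pairing is ignored.** True one-sided size = 1 − Φ(1.645 / √(1 − r)): 2.5% at r = 0.3, 1.0% at 0.5, 0.1% at 0.7.

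**3. Power if pairing is ignored, against paired.** Unpaired test: Φ((0.3 / (SD × √(2/n)) − 1.645) / √(1 − r)). Paired test: Φ(0.3 × √n / (SD × √(2(1 − r))) − 1.645). At n=24:

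| Score SD | Unpaired, r = 0 | Unpaired, r = 0.5 | Paired, r = 0.5 |
|---|---|---|---|
| 0.5 | 67% | 73% | 90% |
| 0.84 | 34% | 28% | 54% |
| 1.0 | 27% | 20% | 43% |
| 1.41 (scores 0-4 equally likely) | 18% | 10% | 27% |

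**4. All three tests on integer scores.** Simulation, 40,000 trials, n=24; scores rounded and clipped to 0-4, latent mean 2.3 and SD 0.8 (both assumed), realised SD 0.84, shift 0.3, one-sided 0.05; McNemar in its large-sample form:

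| Observed r | Mantel-Haenszel, unpaired | McNemar, cut at 2 | Mantel-Haenszel, woman as stratum |
|---|---|---|---|
| 0.44 | 28% | 32% | 47% |
| 0.62 | 25% | 36% | 61% |
| 0.71 | 23% | 42% | 72% |

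With no true shift, the unpaired test rejected in 1.6%, 0.6% and 0.2% of trials; the other two rejected in about 5%.

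**5. What pairing can and cannot restore.** Paired power, one-sided, by SD of change:

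| SD of change | n=24 | n=50 |
|---|---|---|
| 0.68 | 70% | 93% |
| 0.8 | 58% | 84% |
| 1.0 | 43% | 68% |

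At score SD 1.0, an SD of change of 0.678 requires r of at least 1 − 0.678²/2 = 0.77.

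**6. Sidedness.** With a two-sided 0.05 test (z = 1.96), as a one-degree-of-freedom chi-square is in effect, the 70% at n=24 and SD of change 0.68 falls to 58%.

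**The case against.** - **A reader might infer that the plan stratifies this test by site rather than by woman.** The documents do not say so. The site wording follows the treated-versus-non-participant table and applies only if other sites join. For biopsy versus surgery no strata are given. Matching by woman is a standard use of Mantel-Haenszel, so silence is not a decision to treat the specimens as independent. What stands is that the pairing is unspecified.
- **The plan already has a formal paired test.** It does, in McNemar's test. But that test discards the full score, and the power statement is not attached to it.
- **A reader might infer that the stated power is not delivered.** That cannot be shown. With no SD given, 70% is reached even with independent specimens if the score SD is 0.48 or less. Read as a difference in proportions, 50% versus 20%, 0.3 gives n = 24 per group and 71% one-sided. The text, however, speaks of a score difference and states no proportions, and that calculation also assumes independent groups.
- **Accrual of 50-60 eases the problem.** It does: the unpaired limit rises to SD 0.69 at n=50. At SD 0.84 and r = 0, unpaired power at n=50 is Φ(0.3 / (0.84 × 0.2) − 1.645) = 56%, still below 70%.
- **The error is conservative.** True: the risk is a missed effect, not a false positive.

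**Conclusion.** The point holds as an under-specified analysis with an unsupported power figure. Section 15.2 does not say that the biopsy-versus-surgery Mantel-Haenszel test is matched by woman, its formal paired test dichotomises the score, and so no planned final test uses both the pairing and the full score. The power above 70% at n=24 is conditional on a spread that the documents do not give: a score SD of at most about 0.48 with independent specimens, or an SD of change of at most 0.68 when paired.

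Under the assumed score distribution in step 4, a paired full-score test has 47-72% power, against 23-28% for the unpaired test and 32-42% for McNemar. These figures depend on the assumed SD, correlation and mean; the ordering requires a clearly positive within-woman correlation. The documents do not support the stronger conclusions that the test is stratified by site or that the trial is shown to be underpowered.

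**What to change.** In Section 15.2:

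1. Name one paired full-score test as the biopsy-versus-surgery analysis: mean-score Mantel-Haenszel with each woman as a stratum, or a signed-rank test on within-woman change. Make McNemar at the cut of 2 supportive. Any site strata stay with the treated-versus-non-participant test.
2. Use the same sidedness in the power statement and in the analysis.
3. Replace the single power figure with one conditional on the SD of within-woman change. One-sided at n=24: 70% at 0.68, 58% at 0.8, 43% at 1.0. At n=50: 70% up to 0.98. State which SD is assumed and why.

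The cost is a few sentences, with no new patients, specimens or assays. The stated power becomes conditional and may look less favourable. Pairing alone does not secure 70%; that still depends on the SD of change and on how many women are enrolled.
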